#### **Email**

Please enter your TAMU email ([contact]) so we can contact you for future follow phases of the study if you qualify. Remember, everything you reported here is completely confidential. (free text)

### **Procedure**

All data will be collected on qualtrics. Interested individuals will sign up using the online subject pool, SONA. Part 1 will be completed online, either in the lab or at their own personal computer. After electronically confirming consent (using the provided informed consent sheet from TAMU Research Compliance and Biosafety), participants will complete demographics, followed by the Alcohol Use Disorder Identification Test, a measure of perceived behavioral control, a measure of delay-discounting, the Daily Drinking Questionnaire-Revised, the Young Adult Alcohol Consequences Questionnaire, Protective Behavioral Strategies (PBS), the Personal Assessment of Responsible Drinker Identity Scale, Alcohol Use Contemplation/Intention measure. After these measures have been completed, participants will then be randomly assigned to one of four conditions. In one condition, participants will be asked to only write about a negative drinking event. In the second condition, participants will be asked to write about a negative drinking event in addition to recalling facts about the same event. In the third condition, participants will be asked to write about a negative drinking event and will then complete a counterfactual task. The task will ask the individuals to list three counterfactual strategies about the negative event, future situations these strategies could be used, as well as obstacles to using the strategies. The task will wrap up by asking these participants to indicate intention to use those strategies in the future. In the fourth condition, participants will be asked to complete the Personalized Normative Feedback (PNF). Participants in all conditions will complete perceptions of protective behavioral strategy norms questions, the Alcohol Use Contemplation/Intentions measure, a measure of perceived behavioral control as well as intentions to use protective behavioral strategies.

All follow up parts will be either online or in the lab, one week apart. Participants will indicate, for each day the previous week (Sunday, Saturday, Friday, Thursday, Wednesday, Tuesday, Monday), what they were doing, their general location, if they consumed alcohol that day, and the extent to which they experienced a list of situations. Following this, all participants will then indicate the extent that they used the list of PBS. For those who had been randomly assigned to the counterfactual condition in Part 1, they will complete additional measures: indicating the use of the counterfactual strategies that the participant came up with in Part 1 and their intention to use these counterfactual strategies over the next week. Finally, all participants will complete a measure of perceived behavioral control, rate intentions to use PBS in the next week, and answer the protective behavioral strategy norms questions. In follow up sessions 4 and 6, participants will also complete the Personal Assessment of Responsible Drinker Identity Scale and the delay discounting task. Email information will be completed at the end of each part. A page displaying additional resources will also be displayed. All participants will finish the study by completing a debriefing task after the final follow up.

- Drugs
- Devices
- Supplements

Significance:

.....

The present research could have a variety of implications for clinical psychology research, treatment regimens for alcohol, and college alcohol campaigns. Since counterfactual thinking is a naturally occurring and automatic reaction to negative events, they are likely to influence individuals who have had a negative experience while drinking. However, counterfactuals can produce positive outcomes, such as meaning-making and increased intentions, as well as negative outcomes, such as rumination and regret. Investigating how these naturally occurring thoughts might be used to aid in behavioral strategies towards alcohol use, and decision-making more broadly, could help to inform plans to curb young adult binge drinking.

Subjects, enrollment, recruitment, inclusion and exclusion criteria, and informed consent:

## Participants

Participants will be recruited via the Texas A&M University online research subject pool (SONA). To be included in the study procedures and subsequent data analyses, participants must be 18 or older and complete all parts. There are no exclusion criteria for participation in the baseline study (part 1). However, participants who do not follow the instructions for the specific writing task will be unable to sign-up for the remaining follow up sessions (Parts 2-6) and will be excluded from the final data analyses. For Part 1, they will be provided with a link to the Qualtrics survey (if completing online) or will sign up via SONA for an in-person lab session. For Parts 2-5, participants will be able to sign up after successfully completing the prior session; however, if they do not successfully complete the writing prompt requirements outlined in Part 1, then they will be unable to continue on to the remaining study sessions (parts 2-6). If this is the case, then the researchers involved in this study will contact participants to let them know their remaining follow-up sessions will be canceled, but will still receive credit for what they have completed.

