#### 9.4 Inclusion/Exclusion Criteria

What are the inclusion and exclusion criteria for study participation?

The only inclusion criterion for participation is the minimum age requirement (18 years old).

There are no exclusion criteria for participation in the baseline study (part 1). However, participants who do not follow the instructions for the specific writing task will be unable to sign-up for the remaining follow up sessions (Parts 2-6) and will be excluded from the final data analyses. For Part 1, they will be provided with a link to the Qualtrics survey. For Parts 2-5, participants will be able to sign up after successfully completing the prior session; however, if they do not successfully complete the writing prompt requirements outlined in Part 1, then they will be unable to continue on to the remaining study sessions (parts 2-6). If this is the case, then the researchers involved in this study will contact participants to let them know their remaining follow-up sessions will be canceled, but will still receive credit for what they have completed.

Do the exclusion criteria exclude specific populations or individuals based on gender, culture, language, economics, race, or ethnicity?

Yes  No

If Yes, then justify each exclusion:

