#### 9.6 Experience of Subjects

Describe the experience of subjects while participating in this research. (Please describe what the participant will experience from the time of learning of the study through completion.)

Participants (undergraduate students at TAMU who need to participate in research for class credit) will sign up to participate in the study by using the SONA subject participation pool. After signing up for Part 1, online participants will receive a link to a Qualtrics survey. Those who are completing the study in lab will participate on the day they signed up for. After reading information about the study and consenting electronically by clicking "I agree", participants will report their TAMU email and then continue on to complete the Part 1 questionnaires. This should take 30 minutes of their time and they will receive 1 credit toward their class research requirement for completing Part 1.

After completing Part 1, participants will be allowed to participate in the follow up sessions (parts 2-6) if they correctly and completely fulfilled the writing task requirements. Each follow up session will be completed through Qualtrics and should not exceed 30 minutes for each follow up session. Each follow up session will take place one week after the previous session. A summary of this is below:

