All participants will be provided with resources that they can utilize should they feel distressed by the study. Instructions will be given to participants before beginning the writing task to leave out specific locations, names, and other personally identifiable information. Finally, the writing about a negative event involving alcohol will be emphasized in the consent forms and participants who do not feel comfortable writing about this will be asked not to participate. They will also be asked to take the study in a place they feel is private and comfortable for them to discuss sensitive topics, such as alcohol use and consumption. In addition, the consent form will remind participants that they are free to discontinue their participation in the study at any time, should they feel uncomfortable or distressed.

What alternatives are available to subjects outside the research (i.e., what is the standard of care, is the research intervention available without participating)?

Students are provided with alternative assignments that can be completed in lieu of research participation by their professors. Furthermore, participants may choose any of the other studies available on the TAMU SONA system as alternatives to participating in our study.

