**\* Skip to the next section if using a Recruitment Pool.**

#### 16.4 How will initial contact be made with potential participants?

All contact regarding study participation will take place via the SONA recruitment pool. Participants will choose to sign up for the study after viewing the options for all studies available for research participation credit on SONA. For Part 1, they will be provided with a link to the qualtrics survey. For Parts 2-6, participants will be able to sign up after successfully completing the prior session; however, if they do not successfully complete the writing prompt requirements outlined in Part 1, then they will be unable to continue on to the remaining study sessions (parts 2-6). If this is the case, then the researchers involved in this study will contact participants to let them know their remaining follow-up sessions will be canceled, but will still receive credit for what they have completed.

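### The writing-task rule removes randomised participants from follow-up and analysis, with no stated counterpart in the PNF arm, and the requirement to complete every part contradicts other sections

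*Protocol*

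**What the plan says.** **Order of events.** In Part 1 (Protocol 8.1, Procedure) baseline measures come first, and "After these measures have been completed, participants will then be randomly assigned to one of four conditions". The condition task follows.

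**Writing rule.** Protocol 8.1 (Participants) says that people who do not follow the writing instructions are "unable to sign-up for the remaining follow up sessions (Parts 2-6) and will be excluded from the final data analyses". Section 9.4 repeats this. Sections 9.6 and 16.4 repeat the bar on follow-up. Section 13.2 describes not qualifying as a failure to follow the writing prompt. Section 9.1 expects some loss of this kind when it justifies enrolling 1500, but gives no rate.

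**Tasks by arm (8.1).**
- Condition 1 writes about a negative drinking event.
- Condition 2 writes about the event, then lists details in up to 10 boxes.
- Condition 3 writes about the event, then gives three counterfactuals, situations for using them and obstacles.
- Condition 4 (PNF) is described only as rating other students' use of protective behavioural strategies (PBS).

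**Completion rule.** Protocol 8.1 (Participants) also states: "To be included in the study procedures and subsequent data analyses, participants must be 18 or older and complete all parts". Section 16.4 adds: "For Parts 2-6, participants will be able to sign up after successfully completing the prior session".

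**SAP.** It contains neither restriction, no analysis population and no missing-data rule. Its only filter is that weeks without drinking are left out. The only level-2 covariate is sex.

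**The concern.** Randomisation makes the arms comparable when people are assigned. Removing people for what they do afterwards, within the assigned arm, can undo that. If the rule acts in the counterfactual arm but not in PNF, a counterfactual arm stripped of poor compliers is compared with an intact PNF arm. That comparison carries the non-inferiority part of Hypothesis 1 and the exploratory equivalence test with margins of d = ±0.20.

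Removed people are never followed, so a different analysis set cannot recover their outcomes. They do have Part 1 baseline and post-task data, so weighting or tipping-point analyses are possible. None is planned, and they would rest on assumptions that cannot be tested.

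The completion rule raises a different problem. Two analysts could build different datasets from these documents, and a literal reading discards weeks that the two-level model can use.

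**Working it through.** **1. What does the writing rule cover?** The wording points both ways.
- Wider reading, the whole condition task: Section 9.4 has "participants who do not follow the instructions for the specific writing task will be unable to sign-up for the remaining follow up sessions", and Section 9.6 has "participants will be allowed to participate in the follow up sessions (parts 2-6) if they correctly and completely fulfilled the writing task requirements".
- Narrower reading, the event prompt only: Section 16.4 has "if they do not successfully complete the writing prompt requirements outlined in Part 1, then they will be unable to continue on", and Section 13.2 also refers to the prompt. In 8.1 that prompt is the negative-event exercise, which Conditions 1–3 share and finish before their tasks diverge.

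**2. Does PNF write?** The task description says no. Section 12.1 reads as if everyone writes ("participants who do not feel comfortable writing about this will be asked not to participate"), and so does 9.6. The exact materials are attachments not in the file.

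| Rule covers | PNF writes the event? | Counterfactual vs control | Counterfactual vs PNF |
|---|---|---|---|
| Event prompt only | Yes | Equal expected failure | Equal expected failure |
| Event prompt only | No | Equal expected failure | At risk |
| Added tasks too | Yes or no | At risk | At risk |

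The equal-failure entries assume that failure is judged without regard to condition, which the available text does not say. In the SAP code the omitted arm is fact listing, so path a compares Condition 3 with Condition 2.

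**3. Size, counterfactual vs PNF.** The documents give no rates, so this is illustration. Shift in an arm's mean = f × g, where f is the failure share among people who drink during follow-up and g is the kept-minus-removed gap in SD.
- f = 10%, g = 0.3: 0.03 SD, or 15% of the 0.20 margin.
- f = 20%, g = 0.4: 0.08 SD, or 40% of the margin.
- g = 0, or all failures non-drinkers: no shift.

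Further assumptions: 375 per arm (1500/4; the ratio is not stated), of whom D = 225–300 (60–80%) drink during follow-up, counted before removal; removal in Condition 3 only; a 95% confidence interval; and the exploratory 0.20 as margin, since Hypothesis 1 states none. Then SE = √(1/(D(1−f)) + 1/D).

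| f, g | SE (D = 225, 300) | Wrong non-inferiority at d = −0.20, kept people higher | Power at d = 0, no gap | Power at d = 0, kept people lower |
|---|---|---|---|---|
| 10%, 0.3 | 0.0969, 0.0839 | 4.9–5.5% | 54–66% | 42–53% |
| 20%, 0.4 | 0.1000, 0.0866 | 12–15% | 52–64% | 22–28% |

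The nominal error is 2.5%. Wrong non-inferiority is 1 − Φ(1.96 − fg/SE). Power is Φ((0.20 − fg)/SE − 1.96), with fg = 0 when there is no gap.

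If the all-parts rule is also applied (step 5), D falls to 225 × 0.590 = 133 up to 300 × 0.774 = 232. Wrong non-inferiority is then 4.3–5.0% and 8.9–12.6%.

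**4. Size, counterfactual vs control, only if the rule covers the added tasks.** Failure of 20% vs 10% with g = 0.4 gives a shift of (0.20 − 0.10) × 0.4 = 0.04 SD. With SE 0.1024 and 0.0887, two-sided type I error is 6.8–7.4% instead of 5%. Equal rates and gaps give no shift.

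**5. Completion rule.** Section 9.4 makes age the only inclusion criterion. Section 9.6 allows fewer follow-ups when the semester runs short, and 15.2 describes waves of 4 or 5 sessions. Read literally, everyone in those waves is excluded. With assumed independent completion of 0.90–0.95 per session, 0.90⁵ = 0.590 and 0.95⁵ = 0.774 finish all five follow-ups. Usable follow-ups per person are 5 × 0.590 = 2.95 to 5 × 0.774 = 3.87. If a missed week did not end follow-up they would be 5 × 0.90 = 4.50 to 5 × 0.95 = 4.75. Both are before the drinking-week filter.

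**The case against.** - **The rule may settle failure before the arms diverge.** This stands for counterfactual versus control. A reader might infer that Hypotheses 1–3 are biased through path a. The documents do not establish that, because the event-prompt reading is open and gives equal expected failure in Conditions 1–3.
- **PNF participants may write too.** This also stands. A reader might infer that PNF escapes the rule altogether. The text supports only that it describes no writing task and no equivalent rule for PNF.
- **The affected test is largely exploratory.** Largely true. The equivalence test is labelled exploratory and the code tests only path a. But Hypothesis 1 itself claims non-inferiority to PNF.
- **Those removed may be non-drinkers, whom the SAP drops anyway.** This limits the size. If 26% fail overall but only 10% of drinkers do, a 0.4 SD gap shifts the mean by 0.04 SD, not 0.10. The AUDIT prescreen (16.14) also enriches for drinkers.
- **An effect among adherers may be what is wanted.** That is legitimate, but the plan does not say so. Dropping non-adherers from some arms also does not yield a randomised comparison of adherers.

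**Conclusion.** The concern holds in limited form. A planned exclusion after randomisation exists, the SAP is silent on it, and its application to PNF is undefined. Counterfactual versus PNF is the comparison most clearly exposed. Counterfactual versus control is exposed only on the wider reading of the rule.

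The amount and sign of any bias cannot be derived from the documents. The 0.03–0.08 SD range rests on assumed failure rates, assumed gaps and removal in Condition 3 only. The 12–15% error rate should not be read as expected: it also borrows the exploratory margin and ignores loss from the all-parts rule, which brings it to 8.9–12.6%.

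The completion rule is a contradiction within the protocol, whatever the retention turns out to be. The 59–77% range is an illustration, not a forecast.

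**What to change.** 1. Let all randomised participants continue to the follow-ups offered to them, whatever their writing performance and even after a missed session. Add a 'none written' option to the Condition 3 follow-ups, which ask people to reread their counterfactuals. Voluntary withdrawal is unchanged.
2. Make the primary analysis by assigned arm, using all available drinking weeks under a stated missing-data assumption.
3. Move writing adherence and completion of all offered parts to sensitivity analyses. State which task adherence covers and how it applies to PNF. Report both analyses for counterfactual versus PNF, since including non-adherers can dilute differences and favour non-inferiority or equivalence.
4. Report writing failures and completion by arm.
5. State one analysis population in Protocol 8.1, 9.4, 9.6, 13.2 and 16.4 and in the SAP, including the shortened waves.

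**Cost.** Text edits, SONA sign-up settings and one survey option; the model is unchanged. If 10–30% of an assumed 1,125 people in Conditions 1–3 (3 × 375) fail, that is about 113–338 people and, at five follow-ups each, up to 563–1,688 extra one-credit sessions.

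**Dilution.** Suppose d = 0.30 among adherers, and non-adherers in each arm gain nothing. At an assumed 225 per arm, power for counterfactual versus control falls from 86% to 82% with 10% non-adherers, or from 81% to 72% with 20%.

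Selection by drinking weeks is also post-randomisation and is not removed by this change.

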## Informed Consent

Participants will be presented with the informed consent form on Qualtrics that will provide an overview of what the study is about, who to contact if any questions arise, and other information deemed necessary to give complete informed consent (see attached form). Participants will be given an option on their computer screen to click "I agree" or "I disagree" to participate in the study. If they agree, then they will continue on and be reminded they are free to discontinue at any time. If they disagree, then they will be taken to an exit screen and prompted to close the browser. Participants will be given as much time as they need to fully read the form as well as email the researchers any questions.

Will audio recordings be collected?

Yes  No

Will visual images be collected?

Yes  No

If visual images will be collected, are they full, facial identifiable images?

Yes  No

## 8.2 Locations

List locations or facilities where the research will be conducted (e.g. building name, physical address).

Research will be conducted online via a survey website (i.e. Qualtrics). Participants will either complete the online survey in the lab (Psychology Department) or, for those who are completing the study remotely, they will be given a link after signing up, and can complete it wherever they feel comfortable completing the study.

Are any of the locations listed above non-Texas A&M facilities?

Yes  No

What is the role of each location?

Data collection site (lab computer or personal computer/other device participant has access to at their location).

Is the PI of this IRB study application the lead investigator of a multicenter study (i.e. the study is taking place at multiple institutions that are obtaining their own IRB approval and you are coordinating and overseeing the research)?

Yes  No

Has IRB approval been sought at another institution?

Yes  No

Please submit the Site Authorization letter(s) with this application as a study document or indicate when site authorization will be obtained. Guidance is available at <http://rcb.tamu.edu/humansubjects/resources/site-authorization-letter>

### 8.3 Other Committee Approvals

Select all that apply.

- None
- Animal Use
- Biohazards
- Chemical
- Radiation
- Other

If any committee approvals apply, please provide the permit number and approval date.

## 9.0

### Study Population

#### 9.1 Number of Participants

Approximately how many subjects do you plan to enroll?

1500

Provide the rationale for the number of subjects requested (for example, power analysis, sponsor requirements, etc.).

To have adequate statistical power to compare across the three conditions, assuming that not all participants will qualify after the baseline study and there will be some participant attrition across the follow up sessions.

Will human subjects be used from the Qatar population?

Yes  No

**\* If Yes, then approval by an IRB in Qatar may also be required.**

Will human subjects be used from another international population?

Yes  No

**\*If Yes, then approval by an international review board or government may also be required.**

Will human subjects be used from a Native American population?

Yes  No

**\*If Yes, then approval by a tribal IRB(s) may also be required.**

If Yes for research in Qatar, in another country, or with Native Americans, provide justification for that research being conducted in that particular community.

#### 9.2 Provide the age groups being enrolled into this study (Note the consent documents required for each age group listed in parentheses):

- 0-6 (parental consent only, Pediatric Assessment required for Clinical Trials)
- 7-11 (child's assent plus parental permission, Pediatric Assessment required for Clinical Trials)
- 12-17 (consent plus parental permission, Pediatric Assessment required for Clinical Trials)
- 18+ (consent only)

Enter the specific age range for study population (if overlap or specific within a category):

